6.3 Assessing and Recording Adverse Events

An adverse event is defined as any untoward medical occurrence in a patient or clinical investigation subject administered a pharmaceutical product and which does not necessarily have to have a causal relationship with this treatment. An adverse event can therefore be any unfavorable and unintended sign (including an abnormal laboratory finding, for example), symptom, or disease temporally associated with the use of a medicinal product or protocol-specified procedure, whether or not considered related to the medicinal product or protocol-specified procedure. Any worsening (i.e., any clinically significant adverse change in frequency and/or intensity) of a preexisting condition that is temporally associated with the use of the Merck's product, is also an adverse event.

Changes resulting from normal growth and development that do not vary significantly in frequency or severity from expected levels are not to be considered adverse events.

Product: Pembrolizumab and Lenalidomide
Protocol/Amendment No.: Version 3.1 July 18th, 2017

Examples of this may include, but are not limited to, teething, typical crying in infants and children and onset of menses or menopause occurring at a physiologically appropriate time.

Merck product includes any pharmaceutical product, biological product, device, diagnostic agent or protocol-specified procedure, whether investigational (including placebo or active comparator medication) or marketed, manufactured by, licensed by, provided by or distributed by Merck for human use.

Adverse events may occur during the course of the use of Merck product in clinical trials or within the follow-up period specified by the protocol, or prescribed in clinical practice, from overdose (whether accidental or intentional), from abuse and from withdrawal.

Adverse events may also occur in screened subjects during any pre-allocation baseline period as a result of a protocol-specified intervention, including washout or discontinuation of usual therapy, diet, placebo treatment or a procedure.

Progression of the cancer under study is not considered an adverse event unless it is considered to be drug related by the investigator.

All adverse events will be recorded from the time the consent form is signed through 30 days following cessation of treatment and at each examination on the Adverse Event case report forms/worksheets.

6.3.1 Investigator reporting: notifying the study sponsor, NYU IRB, and Perlmutter Cancer Center Clinical Trials Office

The following describes events must be reported to the study sponsor in an expedited fashion.

Initial Report: within 24 hours:

The following events must be reported to the PCC Clinical Trials Office and the study sponsor by telephone within 24 hours of awareness of the event:

- Unanticipated problems related to study participation,
- Serious adverse events, regardless of whether they are unexpected.

Product: Pembrolizumab and Lenalidomide
Protocol/Amendment No.: Version 3.1 July 18th, 2017

Additionally, an FDA Form 3500A (MEDWATCH Form) must be completed by the investigator and faxed/mailed to the study sponsor and PCC Clinical Trials Office within 24 hours. The investigator shall maintain a copy of the MEDWATCH Form on file at the study site.

[contact]

AND

[name]
[name]
[name]
[contact]
Email: [contact]

Follow-up report: within 48 hours:

As a follow-up to the initial report, within the following 48 hours of awareness of the event, the investigator shall provide further information, as applicable, on the unanticipated device event or the unanticipated problem in the form of a written narrative. This should include a copy of the completed Unanticipated Problem form, and any other diagnostic information that will assist in the understanding of the event. Significant new information on ongoing unanticipated adverse device effects shall be provided promptly to the study sponsor. All report forms must be signed and dated by the Principal Investigator. If the Principal Investigator is not available at the time of the initial report, then the form can be submitted by a Sub-Investigator. This form should be reviewed by the Principal Investigator, whom sign/date initial report upon return.

Product: Pembrolizumab and Lenalidomide
Protocol/Amendment No.: Version 3.1 July 18th, 2017

Other Reportable events:

- **Deviations from the study protocol**

Deviations from the protocol must receive both Sponsor and the investigator's IRB approval before they are initiated. Any protocol deviations initiated without Sponsor and the investigator's IRB approval that may affect the scientific soundness of the study, or affect the rights, safety, or welfare of study subjects, must be reported to the Sponsor and to the investigator's IRB as soon as a possible, but *no later than 5 working days* of the protocol deviation.

- ***Withdrawal of IRB approval***

An investigator shall report to the sponsor a withdrawal of approval by the investigator's reviewing IRB as soon as a possible, but *no later than 5 working days* of the IRB notification of withdrawal of approval.

6.3.2 Investigator reporting: notifying the IRB

Federal regulations require timely reporting by investigators to their local IRB of unanticipated problems posing risks to subjects or others. The following describes the NYULMC IRB reporting requirements, though Investigators at participating sites are responsible for meeting the specific requirements of their IRB of record. The NYU IRB address is:

NYU School of Medicine IRB
[name]
[name]

Product: Pembrolizumab and Lenalidomide
Protocol/Amendment No.: Version 3.1 July 18th, 2017

Report promptly, but no later than 5 working days:

Researchers are required to submit reports of the following problems promptly but no later than 5 working days from the time the investigator becomes aware of the event:

- ***Unanticipated problems including adverse events that are unexpected and related***
 - *Unexpected: An event is “unexpected” when its specificity and severity are not accurately reflected in the protocol-related documents, such as the IRB-approved research protocol, any applicable investigator brochure, and the current IRB-approved informed consent document and other relevant sources of information, such as product labeling and package inserts.*
 - *Related to the research procedures: An event is related to the research procedures if in the opinion of the principal investigator or sponsor, the event was more likely than not to be caused by the research procedures.*
 - *Harmful: either caused harm to subjects or others, or placed them at increased risk*

Other Reportable events:

The following events also require prompt reporting to the IRB, though ***no later than 5 working days***:

- ***Complaint of a research subject*** when the complaint indicates unexpected risks or the complaint cannot be resolved by the research team.
- ***Protocol deviations or violations*** (includes intentional and accidental/unintentional deviations from the IRB approved protocol) for any of the following situations:
 - *one or more participants were placed at increased risk of harm*

Product: Pembrolizumab and Lenalidomide
Protocol/Amendment No.: Version 3.1 July 18th, 2017

- *the event has the potential to occur again*
- *the deviation was necessary to protect a subject from immediate harm*
- ***Breach of confidentiality***
- ***Incarceration of a participant*** when the research was not previously approved under Subpart C and the investigator believes it is in the best interest of the subject to remain on the study.
- ***New Information indicating a change to the risks or potential benefits*** of the research, in terms of severity or frequency. (e.g. analysis indicates lower-than-expected response rate or a more severe or frequent side effect; Other research finds arm of study has no therapeutic value; FDA labeling change or withdrawal from market)

Reporting Process

The reportable events noted above will be reported to the IRB using the form: “Reportable Event Form” or as a written report of the event (including a description of the event with information regarding its fulfillment of the above criteria, follow-up/resolution and need for revision to consent form and/or other study documentation).

Copies of each report and documentation of IRB notification and receipt will be kept in the Clinical Investigator’s study file.

At the time of each annual review any protocol deviations stated above, such as dose-reductions (even if done in accordance with protocol guidelines) must be reported to the IRB.

6.3.3 Sponsor reporting: Notifying the FDA

The study sponsor is required to report certain study events in an expedited fashion to the FDA. These written notifications of adverse events are referred to as IND safety reports. The

Product: Pembrolizumab and Lenalidomide
Protocol/Amendment No.: Version 3.1 July 18th, 2017

following describes the safety reporting requirements by timeline for reporting and associated type of event:

- ***Within 7 calendar days*** (via telephone or facsimile report)

Any study event that is:

- associated with the use of the study drug
- unexpected,
- fatal or life-threatening

- ***Within 15 calendar days*** (via written report)

Any study event that is:

- associated with the use of the study drug,
- unexpected, and
- serious, but not fatal or life-threatening

-or-

- a previous adverse event that was not initially deemed reportable but is later found to fit the criteria for reporting (reporting within 15 calendar days from when event was deemed reportable).

Any finding from tests in laboratory animals that:

- Suggest a significant risk for human subjects including reports of mutagenicity, teratogenicity, or carcinogenicity.

Additional reporting requirements

Sponsors are also required to identify in IND safety reports all previous reports concerning similar adverse events and to analyze the significance of the current event in light of the previous reports.

Product: Pembrolizumab and Lenalidomide
Protocol/Amendment No.: Version 3.1 July 18th, 2017

Reporting Process

Adverse events may be submitted on FDA Form 3500A (MEDWATCH Form), or in a narrative format. The contact information for submitting IND safety reports is noted below:

Email: [contact]

[contact]

6.3.4 Definition of an Overdose for This Protocol and Reporting of Overdose to the Sponsor and to Merck

For purposes of this trial, an overdose of pembrolizumab will be defined as any dose of 1,000 mg or greater (≥ 5 times the indicated dose). No specific information is available on the treatment of overdose of pembrolizumab. Appropriate supportive treatment should be provided if clinically indicated. In the event of overdose, the subject should be observed closely for signs of toxicity. Appropriate supportive treatment should be provided if clinically indicated.

If an adverse event(s) is associated with (“results from”) the overdose of a Merck product, the adverse event(s) is reported as a serious adverse event, even if no other seriousness criteria are met.

If a dose of Merck’s product meeting the protocol definition of overdose is taken without any associated clinical symptoms or abnormal laboratory results, the overdose is reported as a non-serious Event of Clinical Interest (ECI), using the terminology “accidental or intentional overdose without adverse effect.”

All reports of overdose with and without an adverse event must be reported within 24 hours to the Sponsor and within 2 working days hours to Merck Global Safety. (Attn: Worldwide Product Safety; [contact])

6.3.5 Reporting of Pregnancy and Lactation to the Sponsor and to Merck

Although pregnancy and lactation are not considered adverse events, it is the responsibility of investigators or their designees to report any pregnancy or lactation in a subject (spontaneously reported to them), including the pregnancy of a male subject's female partner that occurs during the trial or within 120 days of completing the trial, or 30 days following cessation of treatment if the subject initiates new anticancer therapy,

Product: Pembrolizumab and Lenalidomide
Protocol/Amendment No.: Version 3.1 July 18th, 2017

whichever is earlier. All subjects and female partners of male subjects who become pregnant must be followed to the completion/termination of the pregnancy. Pregnancy outcomes of spontaneous abortion, missed abortion, benign hydatidiform mole, blighted ovum, fetal death, intrauterine death, miscarriage and stillbirth must be reported as serious events (Important Medical Events). If the pregnancy continues to term, the outcome (health of infant) must also be reported.

Such events must be reported within 24 hours to the Sponsor and within 2 working days to Merck Global Safety. (Attn: Worldwide Product Safety; [contact])

6.3.6 Immediate Reporting of Adverse Events to the Sponsor and to Merck

6.3.1.1 Serious Adverse Events

A serious adverse event is any adverse event occurring at any dose or during any use of Merck's product that:

- Results in death;
- Is life threatening;
- Results in persistent or significant disability/incapacity;
- Results in or prolongs an existing inpatient hospitalization;
- Is a congenital anomaly/birth defect;
- Is a new cancer (that is not a condition of the study);
- Is associated with an overdose;
- Is another important medical event

Refer to Table 7 for additional details regarding each of the above criteria.

Any serious adverse event, or follow up to a serious adverse event, including death due to any cause other than progression of the cancer under study that occurs to any subject from the time the consent is signed through 90 days following cessation of treatment, or the initiation of new anti-cancer therapy, whichever is earlier, whether or not related to Merck product, must be reported within 24 hours to the Sponsor and within 2 working days to Merck Global Safety.

Non-serious Events of Clinical Interest will be forwarded to Merck Global Safety and will be handled in the same manner as SAEs.

Product: Pembrolizumab and Lenalidomide
Protocol/Amendment No.: Version 3.1 July 18th, 2017

Additionally, any serious adverse event, considered by an investigator who is a qualified physician to be related to Merck product that is brought to the attention of the investigator at any time outside of the time period specified in the previous paragraph also must be reported immediately to the Sponsor and to Merck.

SAE reports and any other relevant safety information are to be forwarded to the Merck Global Safety [contact]

A copy of all 15 Day Reports and Annual Progress Reports is submitted as required by FDA, European Union (EU), Pharmaceutical and Medical Devices agency (PMDA) or other local regulators. Investigators will cross reference this submission according to local regulations to the Merck Investigational Compound Number (IND, CSA, etc.) at the time of submission. Additionally investigators will submit a copy of these reports to Merck & Co., Inc. (Attn: Worldwide Product Safety; [contact]) at the time of submission to FDA.

All subjects with serious adverse events must be followed up for outcome.

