	Is an overdose (whether accidental or intentional). Any adverse event associated with an overdose is considered a serious adverse event. An overdose that is not associated with an adverse event is considered a non-serious event of clinical interest and must be reported within 24 hours.	
Other important medical events that may not result in death, not be life threatening, or not require hospitalization may be considered a serious adverse event when, based upon appropriate medical judgment, the event may jeopardize the subject and may require medical or surgical intervention to prevent one		

	of the outcomes listed previously (designated above by a †).	
Duration	Record the start and stop dates of the adverse event. If less than 1 day, indicate the appropriate length of time and units	
Action taken	Did the adverse event cause the Merck product to be discontinued?	
Relationship to test drug	
Did the Merck product cause the adverse event? The determination of the likelihood that the Merck product caused the adverse event will be provided by an investigator who is a qualified physician. The investigator's signed/dated initials on the source document or worksheet that supports the causality noted on the AE form, ensures that a medically qualified assessment of causality was done. This initialed document must be retained for the required regulatory time frame. The criteria below are intended as reference guidelines to assist the investigator in assessing the likelihood of a relationship between the test drug and the adverse event based upon the available information.
 
The following components are to be used to assess the relationship between the Merck product and the AE; the greater the correlation with the components and their respective elements (in number and/or intensity), the more likely the Merck product caused the adverse event (AE):
	
	Exposure	Is there evidence that the subject was actually exposed to the Merck product such as: reliable history, acceptable compliance assessment (pill count, diary, etc.), expected pharmacologic effect, or measurement of drug/metabolite in bodily specimen?
	Time Course	
Did the AE follow in a reasonable temporal sequence from administration of the Merck product?
 
Is the time of onset of the AE compatible with a drug-induced effect (applies to trials with investigational medicinal product)?

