	Likely Cause	Is the AE not reasonably explained by another etiology such as underlying disease, other drug(s)/vaccine(s), or other host or environmental factors

Relationship to Merck product (continued)	The following components are to be used to assess the relationship between the test drug and the AE: (continued)	
	Dechallenge	
Was the Merck product discontinued or dose/exposure/frequency reduced?
 
If yes, did the AE resolve or improve?
 
If yes, this is a positive dechallenge. If no, this is a negative dechallenge.
 
(Note: This criterion is not applicable if: (1) the AE resulted in death or permanent disability; (2) the AE resolved/improved despite continuation of the Merck product; or (3) the trial is a single-dose drug trial); or (4) Merck product(s) is/are only used one time.)

	Rechallenge	
Was the subject re-exposed to the Merck product in this study?
 
If yes, did the AE recur or worsen?
 
If yes, this is a positive rechallenge. If no, this is a negative rechallenge.
 
(Note: This criterion is not applicable if: (1) the initial AE resulted in death or permanent disability, or (2) the trial is a single-dose drug trial); or (3) Merck product(s) is/are used only one time).
 
NOTE: IF A RECHALLENGE IS PLANNED FOR AN ADVERSE EVENT WHICH WAS SERIOUS AND WHICH MAY HAVE BEEN CAUSED BY THE MERCK PRODUCT, OR IF REEXPOSURE TO THE MERCK PRODUCT POSES ADDITIONAL POTENTIAL SIGNIFICANT RISK TO THE SUBJECT, THEN THE RECHALLENGE MUST BE APPROVED IN ADVANCE BY THE U.S. CLINICAL MONITOR AS PER DOSE MODIFICATION GUIDELINES IN THE PROTOCOL.

	Consistency with Trial Treatment Profile	
Is the clinical/pathological presentation of the AE consistent with previous knowledge regarding the Merck product or drug class pharmacology or toxicology?

The assessment of relationship will be reported on the case report forms /worksheets by an investigator who is a qualified physician according to his/her best clinical judgment, including consideration of the above elements.
		
Record one of the following	Use the following scale of criteria as guidance (not all criteria must be present to be indicative of a Merck product relationship).	

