Yes, there is a reasonable possibility of Merck product relationship.	
There is evidence of exposure to the Merck product. The temporal sequence of the AE onset relative to the administration of the Merck product is reasonable. The AE is more likely explained by the Merck product than by another cause.
	
No, there is not a reasonable possibility Merck product relationship	
Subject did not receive the Merck product OR temporal sequence of the AE onset relative to administration of the Merck product is not reasonable OR there is another obvious cause of the AE. (Also entered for a subject with overdose without an associated AE.)
	

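### Table 7 records causality and action taken for pembrolizumab only, so an adverse event due to lenalidomide alone gets the same answer as an unrelated one

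*Combined protocol and SAP*

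**What the plan says.** Table 2 (section 5.3) lists pembrolizumab and lenalidomide as the trial treatment and marks both as experimental. Section 6.2.2.1 (Adverse Event Monitoring) asks that each toxicity be described by, among other things, its causality and the action taken on trial treatment. For the detail it points to the adverse-event section under its old number, 7.2; that section is now 6.3 and contains Table 7.

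Table 7, under Evaluating Adverse Events, is narrower:

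- Relationship: "Did the Merck product cause the adverse event".
- Action taken: "Did the adverse event cause the Merck product to be discontinued".
- The likely-cause row lists as competing explanations "underlying disease, other drug(s)/vaccine(s), or other host or environmental factors".
- Guidance for Yes: "The AE is more likely explained by the Merck product than by another cause".
- Guidance for No includes the case where "there is another obvious cause of the AE".

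Section 6.3 defines a Merck product by Merck's role in making, licensing, supplying or distributing it. Section 9.1 says Merck supplies pembrolizumab and that the study does not supply lenalidomide.

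On reporting, section 6.3.1.1 requires every SAE within its window, related or not. The window ends 90 days after treatment stops or at new anti-cancer therapy, whichever comes first. The section then adds a duty for any SAE considered "to be related to Merck product that is brought to the attention of the investigator at any time outside of the time period specified". Section 6.3.1 (Investigator reporting: notifying the study sponsor) separately lists "Serious adverse events, regardless of whether they are unexpected", to be reported within 24 hours.

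**The concern.** The trial tests a pair of drugs, and a phase 2 secondary objective (section 3.2) is to confirm that the pair is safe. The table that governs how relationship is judged and recorded covers one member of the pair and treats the other as an outside explanation. If treatment-related events are summarised from that answer, events due to lenalidomide alone fall among the unrelated ones and the related count is too low. An action field limited to pembrolizumab would likewise leave out discontinuations of lenalidomide alone.

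**Working it through.** No figure in the plan bears on this point, so the check is a comparison of texts.

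**1. Does the term cover lenalidomide?** Section 6.3 ties it to Merck's role as maker, licensor, supplier or distributor. Section 9.1 gives Merck that role for pembrolizumab only, and nothing in the documents gives it for lenalidomide. Table 7 uses the term 25 times and names lenalidomide 0 times. It says *test drug* three times, including in the row title, but the question in that row and both permitted answers name the Merck product.

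**2. Is Table 7 operative?** It says the investigator will evaluate all adverse events against its items, tells the investigator to record one of two answers, and sends that answer to the case report form or worksheet. The criteria are labelled as guidance and leave room for clinical judgment.

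**3. What answer results?**

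| Investigator believes the event is due to | Table 7 relationship answer |
|---|---|
| pembrolizumab alone | Yes |
| lenalidomide alone | No (another drug is the obvious cause) |
| one or both, not separable | Yes or No, by judgment |
| neither drug | No |

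Rows two and four give the same record. Section 6.2.2.1, which asks about trial treatment, would need them to differ.

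**4. What happens to the action item?** Take a first grade 3 cardiac arrhythmia that is not life-threatening. Table 4 stops lenalidomide permanently. Table 3 has no arrhythmia row; its row for all other drug-related toxicity holds pembrolizumab at grade 3 and allows a restart at grade 0-1. If pembrolizumab is resumed, the action question is answered No although one trial drug was stopped for good. This assumes that each table governs its own drug. The last column of both tables speaks of discontinuing the subject, so the protocol is not fully explicit here.

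**5. Which analyses use the answer?** DLTs (section 5.3.1.3) are attributed to the two-drug regimen on a possible/probable/definite scale, so they do not depend on Table 7. Complete response is not a safety outcome. Section 7 does not say how adverse events will be tabulated. All-cause summaries would be unaffected; only a summary by relationship would be.

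**6. Are SAE reports lost?** Within the window, no: section 6.3.1.1 takes every SAE whatever its cause. After the window, its added clause names only the Merck product, but section 6.3.1 has no product limit and no end date, so a late lenalidomide-related SAE still goes to the sponsor.

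**The case against.** The strongest reply is that this is template wording with little practical effect. The case report form is not in the documents and may already have a lenalidomide field. Lenalidomide information is also implied elsewhere: DLT attribution to the regimen, Table 4 holds, tablet counts at visits (section 6.2.1.7), summaries of dose and time on treatment (section 7.2), and bi-weekly calls on toxicities up to cycle 5 (section 8.1). In a combination the causes often cannot be separated, so per-drug answers would often be duplicates.

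Much of this stands, and it keeps the point small. It does not remove it: even if the form has a lenalidomide field, Table 7 gives no criteria for filling it in, and its present guidance points the other way.

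Two stronger readings are tempting, and the documents do not support either.

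- *A reader might infer that late lenalidomide-related SAEs go unreported.* The late clause in section 6.3.1.1 is introduced as an addition and cancels no other duty. Section 6.3.1 already covers such events, and section 5.2.5 has each site report unexpected problems involving risk to the coordinating office and its IRB. A site that reads one clause in isolation could be misled; that is an ambiguity, not a missing rule.
- *A reader might infer a conflict with the FDA reporting rule*, which applies to events "associated with the use of the study drug". That term is singular and undefined. Section 5.9 uses it for what Merck supplies, while section 6.2.4.1.1 allows a plural. It is therefore not clearly wider than Table 7. The FDA decision is the sponsor's, the sponsor also receives a MedWatch form, and nothing makes the Table 7 answer its only input.

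**Conclusion.** The point holds as a mismatch between section 6.2.2.1, which asks about trial treatment, and Table 7, which records relationship and action for one of the two experimental drugs. It applies to all 26 to 29 planned patients, since all are to receive both drugs. The direction is clear: relationship data taken from Table 7 would understate treatment-related events by those due to lenalidomide alone. The amount cannot be stated, because the documents give no share of events attributable to lenalidomide alone, and the term counts above show coverage, not consequence.

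The conclusion assumes that lenalidomide is outside the Merck-product definition, that sites follow Table 7 as written, and that the case report form adds no lenalidomide entry. It weakens attribution for a secondary safety objective and leaves the complete-response analysis, the DLT analysis and in-window SAE reporting intact. It is a worthwhile improvement, not a threat to the trial's main results.

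**What to change.** In Table 7, record one relationship answer and one action-taken answer for each of pembrolizumab and lenalidomide. Reword the supporting criteria so that the partner drug is not counted as an outside cause of an event. Tell sites to answer Yes for both drugs when the causes cannot be separated.

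As a clarification only, extend the late-SAE clause in section 6.3.1.1 to either study drug for reports to the sponsor, in line with section 6.3.1, and keep the separate duty to notify Merck as it is.

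The cost is a wording change plus one relationship entry and one action entry for lenalidomide, with no extra visits or tests. The downside is some duplicate entries where both drugs are marked Yes. If the case report form already has these fields, only the protocol wording needs to change.
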